10.4. Reporting period

Details of all AEs that are being monitored as defined in sections 10.2 and 10.3 will be documented in source data and, where applicable, reported from the date of randomisation until 30 days post-surgery. SAEs that are judged to be at least possibly related to the use of the SUNPD (unless they are excluded in section 10.3) must still be reported in an expedited manner irrespective of how long after the SUNPD was used the event occurs.

10.5. Reporting Procedure – At UK Sites

10.5.1. Serious Adverse Events

AEs defined as serious and which require reporting as an SAE should be reported on the SUNRISE SAE form. When completing the SAE form, the Investigator will be asked to define the causality and the severity of the AE. This will be on a five-point scale (definitely related; probably related; possibly related; unlikely to be related or unrelated).

On becoming aware that a participant has experienced an SAE, the Investigator (or delegate) must report the SAE to their own Trust in accordance with local practice and to the SUNRISE Trial Office at BCTU.

To report an SAE to the Trial Office at BCTU, the Investigator or delegate(s) must complete, date and sign the trial specific SAE form. The completed form should be faxed or emailed to the BCTU trials team using the number or email address listed below as soon as possible and no later than 24 hours after first becoming aware of the event:

Fax SAE form to: **[name]** **OR** **Email SAE form to:** **[contact]**

On receipt of an SAE form, the BCTU trials team will allocate each SAE a unique reference number and return this via fax or email to the site as proof of receipt. If the site has not received confirmation of receipt of the SAE from the BCTU or if the SAE has not been assigned a unique SAE identification number, the site should contact the BCTU trials team within 1 working day. The site and the BCTU trials team should ensure that the SAE reference number is quoted on all correspondence and follow-up reports regarding the SAE and filed with the SAE form in the ISF.

Where an SAE form has been completed by someone other than the Investigator, the original SAE form will be required to be countersigned by the Investigator to confirm agreement with the causality and severity assessments.

10.5.2. Provision of follow-up information

Participants should be followed up until resolution or stabilisation of the event. Follow-up information should ideally be provided on a new SAE form, using the SAE reference number provided by the BCTU trials team. Once the SAE has been resolved, all follow-up information has been received and the paperwork is complete, the original SAE form that was completed at site must be returned to the SUNRISE Trials Office at BCTU and a copy kept in the ISF.

10.6. Reporting Procedure – UK Trial Office

On receipt of a SAE form from the site, the BCTU trials team will allocate each SAE form with a unique reference number and enter this onto the SAE form in the section for office use only. The SAE form (containing the unique reference number completed) will be forwarded to the site as proof of receipt within 1 working day. The SAE reference number will be quoted on all correspondence and follow-up reports regarding the SAE and filed with the SAE form in the Trial Master File (TMF).

On receipt of an SAE form, the Chief Investigator (CI) or delegate(s) will independently determine the seriousness and causality of the SAE. An SAE judged by the PI or CI or delegate(s) to have a reasonable causal relationship with the intervention will be regarded as a related SAE. The causality assessment given by the PI will not be downgraded by the CI or delegate(s). If the CI or delegate(s) disagrees with the PI's causality assessment, the opinion of both parties will be documented, and where the event requires further reporting, both opinions will be provided in the report.

The CI or delegate(s) will also assess all related SAEs for expectedness. If the event is unexpected (i.e. is not defined in the protocol as an expected event) it will be classified as an unexpected and related SAE. Events which are assessed as both related and unexpected will be classified as Unexpected and Related Serious Adverse Event.

10.7. Reporting to the UK Research Ethics Committee

10.7.1. Unexpected and Related Serious Adverse Events

BCTU will report all events categorised as Unexpected and Related SAEs to the main UK Research Ethics Committees (REC) and Research Governance Team (RGT) at the University of Birmingham within 15 days.

10.7.2. Other safety issues identified during the course of the trial

The main UK RECs and RGT will be notified immediately if a significant safety issue is identified during the course of the trial.

10.7.3. Investigators

Details of all Unexpected and Related SAEs and any other safety issue which arises during the course of the trial will be reported to PIs. A copy of any such correspondence should be filed in the ISF.

10.8. Data Monitoring Committee

The independent Data Monitoring Committee (DMC) will review all SAEs.

10.9. Reporting to third parties

Smith and Nephew will be notified of any SAEs that occur in participants treated with their product. These will be forwarded periodically during the trial and sent as a list of events. No patient identifiable information will be given to the company. Any such requirements must be defined contractually and the arrangements made explicit in the PIS.

11. UK DATA HANDLING AND RECORD KEEPING

11.1. Source Data

In order to allow for the accurate reconstruction of the trial and clinical management of the subject, source data will be accessible and maintained. CRFs will be completed at the time points detailed in Section 9.

Within the SUNRISE Trial, source data is the participant's medical notes generated and maintained at site, the completed Health-related Quality of Life questionnaires and Patient Diaries.

CRFs will be completed in hard copy at each site with originals forwarded to the BCTU when completed. A copy will be kept at the local site. The SUNRISE Trial Office will be responsible for uploading the data from hard copy into the electronic CRF. The electronic CRF will be held on a REDCap database. REDCap is secure online database software that allows research teams to collect and store research data. The software is hosted on University of Birmingham secure servers and only accessible via controlled username and password access.

11.2. Case Report Form Completion

Data reported on each CRF will be consistent with the source data and any discrepancies will be clarified. Staff delegated to complete CRFs will be trained to adhere to GCP. CRF completion guidelines will be sent to all sites and will include guidance on:

- Dates shall be documented as: day / month / year (e.g. 23/Feb/1992) unless otherwise instructed
- Weight and height shall be provided in Kg (e.g. to 60Kg) and cm (e.g. 173cm)
- Trial-specific interpretation of data fields
- Which forms to complete and when
- What to do in certain scenarios, for example when a subject withdraws from the trial
- Missing/incomplete/unknown data
- Completing SAE forms and reporting SAEs
- Protocol and GCP non-compliances

In all cases it remains the responsibility of the site's PI to ensure that the CRF has been completed correctly and that the data are accurate. Where applicable for the trial this will be evidenced by the signature of the site's PI on the CRF or separate declaration form.

For paper CRFs, the completed originals will be submitted to the Trials Office and a copy filed in the ISF. Data collected will be transcribed onto the SUNRISE REDCap database. Sites will return the completed paper CRFs to the SUNRISE Trial Office for entry onto the database.

11.3. Participant completed questionnaires

Participants will complete SF-12 questionnaires at baseline, day 7 and day 30, and EQ-5D-5L questionnaires at baseline, day 7, 14, 21 and day 30.

On discharge from hospital, participants will be asked to complete a daily Patient Diary (which includes the weekly EQ-5D 5L and SF-12 questionnaires) between their discharge from hospital and their Day 30 wound review. These will be completed at home with a weekly phone call or text message from the local research team to remind the participant to complete their diary. The diary will be checked with the participant at their wound review and any missing data points will be clarified.

As part of the diary, participants will complete a Bluebelle wound healing questionnaire before seeing the research team at the Day 30 wound review. It is very important that this is completed by the participant independent from any healthcare professional. If, for any reason, participants have not completed this prior to their Day 30 wound review, they will be asked to complete it independently before the review proceeds with the research team member performing it.

11.4. Data Management

Paper CRFs must be completed, signed/dated and returned to the SUNRISE Trial Office by the PI or an authorised member of the site research team (as delegated on the SUNRISE Trial Site Signature and Delegation Log). Entries on the CRF should be made in ballpoint pen, ideally in black ink, and must be legible. Any errors should be crossed out with a single stroke, the correction inserted and the change initialled and dated. If it is not obvious why a change has been made, an explanation should be written next to the change.

Data reported on each CRF should be consistent with the source data or the discrepancies should be explained. If information is not known, this must be clearly indicated on the CRF. All missing and ambiguous data will be queried. All sections are to be completed. Data clarification forms (DCF) will be sent to sites requesting missing data or clarification of inconsistencies or discrepancies. In all cases, it remains the responsibility of the PI to ensure that the CRF has been completed correctly and that the data are accurate.

Processes will be employed to facilitate the accuracy of the data included in the final report. These processes will be detailed in the trial specific data management plan. Coding and validation will be agreed between the trial's manager, statistician and programmer and the trial database will be signed off once the implementation of these has been assured.

11.5. Data Security

The security of the System is governed by the policies of the University of Birmingham. The University's Data Protection Policy and the Conditions of Use of Computing and Network Facilities set out the security arrangements under which sensitive data should be processed and stored. All studies at the University of Birmingham have to be registered with the Data Protection Officer and data held in accordance with the Data Protection Act. The University will designate a Data Protection Officer upon registration of the study. The Study Centre has arrangements in place for the secure storage and processing of the study data which comply with the University of Birmingham policies.

- The System incorporates the following security countermeasures:
- Physical security measures: restricted access to the building, supervised onsite repairs and storages of back-up tapes/disks are stored in a fire-proof safe.
- Logical measures for access control and privilege management: including restricted accessibility, access-controlled servers, separate storage of non-identifiable data etc.
- Network security measures: including site firewalls, antivirus software, separate secure network protected hosting etc.
- System Management: the System shall be developed by the BCTU Programming Team and will be implemented and maintained by the BCTU Programming Team.
- System Design: the system shall comprise of a database and a data entry application with firewalls, restricted access, encryption and role-based security controls.
- Operational Processes: the data will be processed and stored within the Study Centre (University of Birmingham).
- Data processing: Statisticians will have access to anonymised data.
- System Audit: The System shall benefit from the following internal/external audit arrangements:
 - Internal audit of the system
 - Periodic IT risk assessments
- Data Protection Registration: The University of Birmingham has Data Protection Registration to cover the purposes of analysis and for the classes of data requested. The University's Data Protection Registration number is Z6195856.

11.6. Archiving

Archiving will be authorised by the SUNRISE Trial office on behalf of the Sponsor following submission of the end of trial report. It is the responsibility of the PI to ensure all essential trial documentation and source documents (e.g. signed ICFs, ISF, participants' hospital notes, copies of CRFs etc.) at their site are securely retained for at least 10 years. No documents will be destroyed without prior approval from the SUNRISE Trial Office on behalf of the sponsor.

12. UK QUALITY CONTROL AND QUALITY ASSURANCE

12.1. Site Set-up and Initiation

All participating PIs will be asked to sign the necessary agreements, including a 'Principal Investigator Declaration' and supply a current CV to the SUNRISE Trial Office. All members of the site research team will also be required to sign the SUNRISE Site Signature and Delegation Log, which details which tasks have been delegated to them by the PI.

Prior to commencing recruitment all sites will undergo a process of initiation and will have completed GCP training. Key members of the site research team will be required to attend a Site Initiation Visit (either as a face-to-face meeting or a teleconference/video conference) covering aspects of the trial design, protocol procedures, Adverse Event reporting, collection and reporting of data and record keeping. Sites will be provided with an ISF containing essential documentation, instructions, and other documentation required for the conduct of the trial. The SUNRISE Trial Office must be informed immediately of any change in the site research team.

To quality assure and standardise the use of the SUNPD, all research team members delivering the intervention will undergo training on the use of SUNPD. This training will be provided prior to site opening and will be via teleconference/video conference or a face-to-face meeting. Training will be provided by a combination of members of the Trial Management Group (TMG) and representatives from Smith and Nephew.

Study-specific and SUNPD application training can be disseminated to the other members of the research team by the PI or nominated delegates, such as the associate PI/lead trainee and/or lead research nurse. This will be captured on the SUNRISE Site Signature and Delegation Log and SUNRISE Training Log.

12.2. Monitoring

Sites will be monitored via centralised monitoring from the BCTU. This will include recruitment numbers including the number of patients approached regarding the trial, randomisation numbers and completion of the follow-up period.

12.2.1. On-site Monitoring

On-site monitoring will be carried out as required following a risk assessment and as documented in the monitoring plan. Any monitoring activities will be reported to the trials team and any issues noted will be followed up to resolution. Additional on-site monitoring visits may be triggered, for example by poor CRF return, poor data quality, low SAE reporting rates, excessive number of participant withdrawals or deviations. If a monitoring visit is required, the SUNRISE Trial Office will contact the site to arrange a date for the proposed visit and will provide the site with written confirmation. Investigators will allow the SUNRISE Trial staff access to source documents as requested.

12.2.2. Central Monitoring

SUNRISE will be centrally monitored, however on-site monitoring may occur if triggered. The SUNRISE Trial Office will be in regular contact with the site research team to check on progress and address any queries that they may have. The SUNRISE Trial Office will check incoming CRFs for compliance with the protocol, data consistency, missing data and timing. Sites will be sent DCFs requesting missing data or clarification of inconsistencies or discrepancies at a frequency and intensity determined by the Data Management plan.

12.3. Audit and Inspection

The PI will permit trial-related monitoring, quality checks, audits, ethical reviews, and regulatory inspection(s) at their site, providing direct access to source data/documents. The PI will comply with these visits and any required follow up. Sites are also requested to notify BCTU of any relevant inspections or local audits.

12.4. Notification of Serious Breaches

The sponsor is responsible for notifying the REC of any serious breach of the conditions and principles of GCP in connection with that trial or the protocol relating to that trial. Sites are therefore requested to notify the SUNRISE Trial Office of any suspected trial-related serious breach of GCP and/or the trial protocol. Where the Trials Office is investigating whether or not a serious breach has occurred sites are also requested to cooperate with the Trials Office in providing sufficient information to report the breach to the REC where required and in undertaking any corrective and/or preventive action.

Sites may be suspended from further recruitment in the event of serious and persistent non-compliance with the protocol and/or GCP, and/or poor recruitment. The BCTU will report any major problems identified during monitoring to the Trial Management Group, TSC and the REC. This includes reporting serious breaches of GCP and/or the trial protocol to the REC. A copy of the serious breach report will also be sent to the University of Birmingham Clinical Research Compliance Team at the time of reporting to the REC.

13. END OF TRIAL DEFINITION

The end of trial will be 12 months after the final participant has completed follow-up i.e. 12 months after the date of the Day 30 wound review of the last participant. This will allow sufficient time for the completion of protocol procedures, data collection, data input and data cleaning in preparation for the database to be locked for the clinical data analysis.

13.1. Reporting in the UK

The SUNRISE Trial Office in the UK will notify the UK REC the trial has ended and a summary of the clinical trial report will be provided within 12 months of the end of trial.

A copy of the end of trial notification as well as the summary report is also sent to the University of Birmingham RGT at the time of sending these to the REC.

13.2. Reporting in Australia

The SUNRISE Trial Office in Australia will notify the Australian HREC the trial has ended and a summary of the clinical trial report will be provided within 12 months of the end of trial.

A copy of the end of trial notification as well as the summary report is also sent to the BCTU at the time of sending these to the HREC.

14. STATISTICAL CONSIDERATIONS

14.1. Sample Size

The justification for the sample size is based on data from the ROSSINI trial²⁸, which reported an SSI rate of 25% in the control group. To detect a relative reduction of 40% in SSI rates (i.e. from 25% to 15%, so 10% absolute difference) between groups using the standard method of difference between proportions (2-sided) with 90% power and a type I error rate of 5% (i.e. $\alpha=0.05$), requires 336 participants per group to be randomised, so 672 in total. Assuming and adjusting for a 20% attrition/loss to follow-up rate (based on the death rate in this population being approximately 10% at 30 days; further drop out 10%), 840 participants (420 per group) will need to be recruited. Stata 15 software was used to compute the sample size calculation using the two-sample proportions test.

The 40% reduction correlates with the relative reduction being assessed in other large HTA funded SUNPD trials, such as WHIST.

14.2. Analysis of Outcome Measures

A separate Statistical Analysis Plan (SAP) will be produced and will provide a more comprehensive description of the planned statistical analyses. A brief outline of these analyses is given below.

The primary comparison groups will be composed of those who are randomised to SUNPD versus those randomised to the surgeons' preferred dressing. All analyses will be based on the intention to treat principle, i.e. all participants will be analysed in the groups to which they were randomised irrespective of compliance with the randomised allocated treatment. For all major outcomes, summary statistics and differences between groups (e.g. mean differences, relative risks) will be presented, with 95% confidence intervals and p-values from two-sided tests also given. Analyses will be adjusted for the minimisation variables listed in section 7.3 where possible, and baseline scores (where appropriate). A p-value of <0.05 will be considered statistically significant, and there will be no adjustment for multiple testing.

14.2.1. Primary Outcome Measure

The primary outcome is SSI within 30 days of surgery, as defined by the internationally accredited CDC criteria. This outcome is a binary outcome (i.e. yes/no). The number and percentage of participants reporting an SSI within 30 days of surgery will be reported by treatment group. An adjusted relative risk and 95% confidence interval will be estimated from a mixed effects log-binomial regression model. A risk difference and 95% confidence interval will also be provided. Statistical significance of the treatment group parameter will be determined from the p-value generated by the model.

14.2.2. Secondary Outcome Measures

The secondary outcomes for the trial include continuous, categorical and time to event data items.

Time to Event outcomes (Length of hospital stay after surgery):

These outcomes will be compared between treatment groups using survival analysis methods. Kaplan-Meier survival curves will be constructed for visual presentation of time-to-event comparisons. Mixed effects Cox proportional hazard models will be fitted to obtain treatment effects which will be expressed as hazard ratios with 95% confidence intervals.

Categorical outcomes (Wound complications, Hospital readmission for wound related complication(s), Serious Adverse Events):

For binary secondary outcomes, the number and percentage of participants reporting each outcome will be reported by treatment group. An adjusted relative risk and 95% confidence interval will be estimated from a mixed effects log-binomial regression model.

Continuous outcomes (QoL measures - SF-12 and EQ-5D, Likert scale for pain):

SF-12, EQ-5D-5L and the Likert scale for pain at the site of the primary laparotomy are all continuous data outcomes and therefore will be summarised using means and standard deviations. The data at both day 7 and day 30 will be compared between groups using mixed effects linear regression models to obtain an adjusted mean difference and 95% confidence interval. Data for the EQ-5D-5L is collected at baseline and days 7, 14, 21 and 30, and so as a secondary analysis this outcome will also be analysed using a mixed effects repeated measures model.

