9.2. Secondary Outcomes

- Length of hospital stay after surgery as measured from the date of index surgery to the date of discharge

- Wound complications within 30 days post-surgery as graded by Clavien-Dindo scale (see Appendix 2)
- Hospital re-admission for wound related complications within 30 days. These will include SSIs, wound breakdown/dehiscence, seromas and wound related pain
- Health-related Quality of Life assessed using the validated Short Form-12 (SF-12) questionnaire at baseline, and day 7 and day 30, and the EuroQuol-5 Dimension-5 Level (EQ-5D-5L) at baseline, day 7, day 14, day 21 and day 30. Pain at the site of the primary laparotomy will also be assessed, using a Likert scale of 1-10 at day 7 and day 30
- Serious adverse events up to 30 days
- Cost-effectiveness assessed using a patient diary for patient reported healthcare resource usage. Healthcare usage will be taken directly from the patient diaries and the costs attributable to this will be identified
- Patient acceptability of use of their dressing via an acceptability score using a Likert scale of 1-10 at day 7, reflecting participant's assessment of the acceptability of having the dressing
- In the UK only, Health professional's acceptability of use of SUNPD (via a survey of users). This will focus on the ease of application of the dressing, the care needed to maintain/monitor the dressing while it is in place and an overall assessment of health professional's experience of the dressing

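### Length of stay is committed to Kaplan-Meier curves and a single-event Cox model although in-hospital death precludes discharge; with deaths censored, the curve overstates live discharge by about 2 to 8 percentage points at day 30

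*Protocol*

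**What the plan says.** Section 9.2 of the protocol defines the outcome as "Length of hospital stay after surgery as measured from the date of index surgery to the date of discharge". Section 14.2.2 lists it under "Time to Event outcomes (Length of hospital stay after surgery" and names two methods. For display, "Kaplan-Meier survival curves will be constructed for visual presentation of time-to-event comparisons". For the comparison, "Mixed effects Cox proportional hazard models will be fitted to obtain treatment effects which will be expressed as hazard ratios with 95% confidence intervals".

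Section 14.1 sets the attrition allowance with the words "Assuming and adjusting for a 20% attrition/loss to follow-up rate", and explains the 20% as "based on the death rate in this population being approximately 10% at 30 days; further drop out 10" per cent.

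The protocol gives no rule for a participant who dies before discharge. It names no competing event, cumulative incidence function or censoring rule for this outcome. Section 14.2.4 deals with missing data on the primary outcome only. Section 14.2 describes itself as an outline and refers to a separate SAP, which was not available for this check.

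**The concern.** A participant who dies in hospital can never be discharged alive. Kaplan-Meier handles one event type. If deaths are censored, it assumes that those who died would later have gone home at the same rate as those still in hospital. Its complement then rises towards 100%, although the proportion discharged alive can never exceed one minus in-hospital mortality. The plotted curves and the medians read from them would not describe the probability of leaving hospital alive by a given day, which is how readers will take them.

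The hazard ratio also needs a label. The same Cox model estimates different quantities depending on whether deaths are censored, counted as the end of stay, or kept at risk. These agree when mortality is equal between arms and diverge when it is not. Section 1.1 states that patients with a surgical site infection are twice as likely to die as those without, so an effective dressing could plausibly change mortality.

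**Working it through.** **Plan's own figures.** The protocol states no figure for length of stay, so the only one to reproduce is the sample size that carries the mortality assumption. For 25% v 15%, two-sided 5%, 90% power, pooled variance:

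n = [1.960 × √(2 × 0.20 × 0.80) + 1.282 × √(0.25 × 0.75 + 0.15 × 0.85)]² / 0.10² ≈ 334.2, so 335 per group against the stated 336. Then 672 / (1 − 0.20) = 840. The plan's figures stand. Ten per cent of 840 is about 84 deaths expected by day 30.

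**Size of the curve error.** Inputs from the protocol: the event (discharge) and the order of mortality (10% at 30 days). Assumptions: constant hazards, a median time to discharge m of 8, 12 or 16 days, and a probability d of dying in hospital of 5 to 10%. The protocol gives no distribution of stay, and its 10% is 30-day mortality rather than death before discharge, hence the range.

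- Discharge hazard: λ = ln 2 / m. Total hazard: Λ = λ / (1 − d).
- Kaplan-Meier, deaths censored: 1 − exp(−30λ).
- True proportion discharged alive by day 30: (1 − d) × [1 − exp(−30Λ)].
- True median (half of all participants discharged alive): −ln[1 − 0.5 / (1 − d)] / Λ. The Kaplan-Meier median is m.

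Worked case, m = 12 and d = 0.10: λ = 0.0578 and Λ = 0.0642. Kaplan-Meier gives 1 − exp(−1.733) = 82.3%. The true value is 0.90 × [1 − exp(−1.925)] = 76.9%.

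| m (days) | d | Kaplan-Meier, day 30 | Discharged alive, day 30 | Excess (points, from unrounded values) | Median: Kaplan-Meier v true (days) |
|---|---|---|---|---|---|
| 8 | 5% | 92.6% | 88.8% | 3.7 | 8.0 v 8.2 |
| 8 | 10% | 92.6% | 85.0% | 7.6 | 8.0 v 8.4 |
| 12 | 5% | 82.3% | 79.7% | 2.7 | 12.0 v 12.3 |
| 12 | 10% | 82.3% | 76.9% | 5.4 | 12.0 v 12.6 |
| 16 | 5% | 72.7% | 70.8% | 1.9 | 16.0 v 16.4 |
| 16 | 10% | 72.7% | 68.8% | 4.0 | 16.0 v 16.8 |

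A second parameterisation agrees. Daily hazards of 0.09 (discharge) and 0.010 (death) give 0.9 × [1 − exp(−3.0)] = 85.5% discharged alive, against 1 − exp(−2.7) = 93.3% by Kaplan-Meier, an excess of 7.8 points.

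**Effect on the hazard ratio.** Simulation with 400,000 participants per scenario, no true difference in discharge hazard, m = 12, and assumed in-hospital mortality by arm:

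| Mortality, SUNPD v control | Deaths censored | Death counted as discharge | Deaths kept at risk, never discharged |
|---|---|---|---|
| 10% v 10% | 1.00 | 1.00 | 1.00 |
| 8% v 12% | 1.00 | 0.96 | 1.10 |
| 7% v 13% | 0.99 | 0.93 | 1.14 |
| 12% v 8% | 1.00 | 1.05 | 0.92 |

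The third column can be checked by hand: the ratio of total hazards is (1 − d for control) / (1 − d for SUNPD), for example 0.88 / 0.92 = 0.96. The 0.99 in the second column is simulation noise around 1.00.

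**The case against.** The strongest reply is that coding of deaths belongs in the SAP. Section 14.2 calls itself an outline, and 14.2.2 states no event code or censoring rule. That holds for the missing rule, and the SAP may supply one. It does not fully answer the point, because the protocol names the estimator. A SAP that plots cumulative incidence departs from 14.2.2, and one that follows 14.2.2 with deaths censored inherits the error.

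Three stronger readings are tempting, and the documents do not support them.

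- *The curves and medians must be wrong in both arms.* This depends on coding. If deaths are kept at risk to the end of follow-up as never discharged, and nothing else is censored earlier, the Kaplan-Meier complement equals the cumulative incidence of live discharge.
- *The Cox model is invalid.* With deaths censored it validly estimates the cause-specific hazard ratio for live discharge, and it stays at about 1.00 above even with 7% v 13% mortality.
- *An arm with more early deaths would appear to shorten stay.* This requires death to be coded as discharge. The protocol does not say so: section 9.2 measures to the discharge date, and section 10.3 reports death separately as a serious adverse event.

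Nor are deaths hidden. Serious adverse events are compared by arm under 14.2.2, and the DMC reviews them all under 10.8. Finally, placing the full 10% in hospital takes the upper end of the range, because some deaths by day 30 will follow discharge.

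**Conclusion.** The point stands in limited form. Section 14.2.2 fixes a display method that suits this outcome poorly in a population with substantial expected mortality. With deaths censored in the usual way, day-30 live discharge is overstated by about 2 to 8 percentage points and median stay understated by about 0.2 to 0.8 days, for 5 to 10% in-hospital death, constant hazards and assumed discharge medians of 8 to 16 days. These sizes are illustrative, since the protocol gives neither in-hospital mortality nor a distribution of stay.

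The treatment comparison is sound if the Cox result is read as a cause-specific hazard ratio. It is at risk only if deaths are coded another way and mortality differs between arms. In that case the estimate, and even its direction, depends on a choice the protocol does not declare. The change is worth making, but it concerns one secondary outcome.

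**What to change.** In section 14.2.2, for length of stay:

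- Define the event as discharge alive, with in-hospital death as a competing event.
- Replace the Kaplan-Meier curves with cumulative incidence (Aalen-Johansen) curves for live discharge, and read median stay from them.
- Keep the mixed effects Cox model, and label its result the cause-specific hazard ratio for live discharge.
- Show in-hospital deaths by arm next to it.

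A subdistribution (Fine-Gray) hazard ratio may be added but is not needed. Leaving deaths out of the analysis is not an alternative, because it would conflict with the intention-to-treat statement in section 14.2.

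The cost is small: a few sentences in the protocol and SAP, and slightly more analysis work with standard software. One data point needs attention. Section 10.4 ends routine event reporting at 30 days after surgery, apart from events possibly related to the device. The date of any in-hospital death after day 30 must therefore be recorded for this outcome.
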